**C.5. Measurements.** HVP *Assessment Workers* (registered nurses who can draw blood) who enroll families into standard HVP services, have been trained to screen and recruit eligible families for the proposed project. They will administer the assessments (English or Spanish; **Table 6**) in the families’ homes or at the HVP clinic (as needed) at baseline/enrollment, and after 6mo and 12mo of services. *Home visitors* will be trained to gather interim (objective) weight measurements for the purpose of generating more frequent data points, triangulated with the assessment workers’ measurements.

**Medical and family history.** A thorough family history and physical examination will be conducted at baseline. We will collect demographic data, including socioeconomic status (education, income, eligibility for SNAP).

**Infant growth & waist trajectories.** Weight will be measured on a digital scale (Tanita) accurate to the nearest 5g. Length will be measured to the nearest 0.1 cm using an infanto-meter using the standardized WHO approach,

Table 6. Assessment time points (month of intervention) and key measures							
	Baseline	3	6	9	12	15	18
COVARIATES							
Demographics, household composition, medical history, post-partum depression, activity readiness	X						
MOTHERS							
Weight/height, waist circumference	X	X	X	X	X	X	X
Blood and vitals	X						X
24h diet & activity recall	X		X				X
Feeding and food insecurity	X		X				X
Social support and networks	X		X				X
Home environment	X		X				X
INFANTS							
Weight/length, waist circumference	X	X	X	X	X	X	X
Blood (finger prick)	X						X
24h diet & activity recall (from mother)	X		X				X

including use of staff training modules. Weight and length will be used to calculate weight-for-length and weight-for-age z-scores (WHO Standards), as recommended by the CDC for children <24 mos. Infant growth rates will be examined as the change in WLZ from baseline to follow up (12mo) Waist circumference will be measured at the umbilicus (nearest 1-mm) using a non-stretch measuring tape.

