**Maternal weight & waist circumference.** Weight and height will be measured by Assessment Workers in participants' homes using an electronic scale (Model BWB-800S, Tanita, Portage, MI) and stadiometer (Model PE-AIM-101, Perspective Enterprises) according to standard procedures. Subjects will remove shoes, belts, and heavy outerwear and empty pockets. We will measure height in duplicate and if measurements are not within 0.5 cm, we will obtain a third measurement. The mean of all measurements will be used to calculate BMI. Waist circumference will be measured at the umbilicus to the nearest 1 mm using a non-stretch measuring tape. Maternal obesity prior to pregnancy will be derived from pregravid BMI (recall during pregnancy at recruitment). Gestational weight gain will be defined as the last weight obtained before delivery minus the pregravid recalled weight or the weight recorded at the first prenatal visit during the first trimester using electronic medical record data.

**Maternal diet & activity.** Mothers' dietary intake and activities will be assessed using several items from NHANES (2017), including intake of fruits and vegetables, fried foods, and sugary-sweetened beverages, and time mothers engage in moderate physical activity.

**Maternal social networks & support.** Using egocentric social network methods and EgoWeb software (<http://www.rand.org/methods/egoweb.html>, developed with PI [name]), we will assess the characteristics of the social actors (people, organizations) and relationships that surround mothers. Using standard name generator items, participants are asked to identify 20 important adults in their lives, and then report on the attributes of each person (demographics, health attributes/behaviors) and types of relationships they share. Relationship characteristics of interest include how they know the person (e.g., family, friend from a community program, etc.), frequency of interaction, and provision of support for health behaviors (e.g., encouragement for or co-engagement in specific behaviors). *Social Support measures from the PROMIS database* will be used to assess emotional and instrumental support, and social isolation. Egocentric network data is used to compute network composition variables (e.g., proportions of family/friends in the network), and variables that represent

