## C.6. Analytic Plan.

**General strategy.** Three waves of data will be collected (baseline/enrollment, 6 and 12- months of intervention). Analyses will be carried out according to the intention-to-treat rule consistent with standard practice in most clinical trials. We will conduct standard statistical diagnosis and descriptive statistics of demographic and background variables, and examine frequencies for reasonableness, sparseness (categorical data) and non-normality (continuous variables) of the data. Missing data will be addressed using multiple imputation and/or full information maximum likelihood estimation. Psychometric properties of the study scales will be investigated to ascertain appropriate validity and reliability. Preliminary analyses will test group equivalence on baseline characteristics. Categorical methods of analysis (e.g., cross tabulations, chi-square) will be used for discrete data while *t*-tests will be used for continuous data to test the comparability of the prevention arms. Factors found to be different at baseline will be adjusted for in subsequent analyses. The following **covariates** will be entered in all analyses: home visitor, home visitor experience (years), number of visits, household composition, race/ethnicity, acculturation, mother's age, medical history/gestational diabetes, post-partum depression.

**Social network analysis (SNA).** Network data will be analyzed using SNA packages in R (e.g., SNA, igraph) to produce visualizations and statistics that summarize the characteristics of each mothers' network. We will compute the following network statistics: the proportion of network members that provide specific types of health relevant support, and that engage in specific health behaviors; and the density of supportive relationships within each network (i.e., the number of supportive relationships among network members that are reported, as a proportion of the total number of possible supportive relationships where all network members provide support). These statistics will be computed for each assessment period (as well as change statistics across periods), and included in the analyses, as described below.

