- Anthropometry: body weight, waist circumference, height (mothers/infants)
- Blood pressure (mothers) and blood samples (mothers/infants);
- Variables derived from dietary intake, via recall interviews (mothers as respondents for themselves and for their infants);
- Physical activity via interview/recall (infants) and accelerometers (mothers);
- Social networks and support via questionnaires (mothers);
- Maternal feeding style & practices via questionnaire (mothers);
- Maternal food insecurity via questionnaire (mothers);

**Records.** Mothers' pre-pregnancy weight and infants' birth weight will be obtained from our HVP partner. All other data used for this study will be collected during the implementation of the study protocol.

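### Pre-pregnancy BMI, gestational weight gain and birth weight are collected but not prespecified in the weight and growth models; they can enter only through a baseline significance test

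*Combined protocol and SAP*

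**What the plan says.** **Fixed list.** C.6, General strategy, enters nine covariates in all analyses: home visitor, visitor experience, number of visits, "household composition, race/ethnicity, acculturation", maternal age, medical history including gestational diabetes, and depression after birth. Separately, it compares the arms at baseline with cross-tabulations, chi-square tests and t-tests, and adjusts later analyses for whatever differs.

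**Aim 1 models.** These are multilevel regressions with home visitor as the cluster. The baseline value of each outcome is a covariate. No other prognostic variable is named there.

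**What is collected.** C.5, on maternal weight, says: "Maternal obesity prior to pregnancy will be derived from pregravid BMI (recall during pregnancy at recruitment". It continues: "Gestational weight gain will be defined as the last weight obtained before delivery minus the pregravid recalled weight", or minus a first-trimester prenatal weight from the medical record. The Records paragraph (Human Subjects, section A) adds: "Mothers' pre-pregnancy weight and infants' birth weight will be obtained from our HVP partner".

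**Schedule.** The covariate row of Table 6 reads "Demographics, household composition, medical history, post-partum depression, activity readiness". It names none of the three perinatal variables and no acculturation measure.

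**The concern.** The three variables describe weight history before the study baseline, and the primary comparisons concern later weight and growth. The plan gives them no prespecified role. Whether any of them is adjusted for depends on a hypothesis test of something randomisation already settles, namely whether the arms differ beyond chance. That rule can leave out a strongly prognostic variable that happens to be balanced and admit a weak one that happens not to be. It also makes the final model depend on the data. Only 30 home visitors are randomised (Power Analysis), and families are matched to visitors on ethnicity, race and language, so some imbalance in prior weight is a realistic prospect. At stake are some precision and a firmly prespecified Aim 1 model, not the validity of the arm comparison.

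**Working it through.** **1. Routes into the model.**

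| Variable | Collected | Fixed list (C.6) | Named in Aim 1 | Other route |
|---|---|---|---|---|
| Pre-pregnancy weight/BMI | C.5; Records | No | No | Baseline test |
| Gestational weight gain | C.5 | No | No | Baseline test |
| Birth weight | Records | No | No | Baseline test |

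**2. How often the test would admit them.** Assume a baseline variable has the plan's own design effect of 1.4 to 1.8. An unclustered 5% test then has a true rejection rate under randomisation of 2 × [1 − Φ(1.96/√DEFF)].
- DEFF 1.4: 1.96/1.183 = 1.66, giving 9.8%.
- DEFF 1.8: 1.96/1.342 = 1.46, giving 14.4%.

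The test flags too often for its nominal level, yet each variable would still be left out in roughly 86% to 90% of randomisations, whatever its prognostic value.

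**3. What baseline adjustment leaves uncovered.** Infants enter at 6 months. Section B.3 cites rapid gain in the first 4 to 6 months as a predictor of later overweight. Baseline size alone does not show that gain; birth weight together with baseline size does. For mothers, the same baseline weight can reflect retained pregnancy weight or long-standing weight, and only a pre-pregnancy value separates them.

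**4. The plan's own figure.** The Power Analysis states a detectable Cohen's f of .17 to .20 with N = 200 and design effects 1.4 to 1.8. It does not give the power, the number of repeated measures or their correlation for this figure. Assuming 80% power, 3 measures and correlation .3, the repeated-measures between-groups F test gives f = .172 and .196, which matches. With correlation .5 it gives .193 and .219. The stated inputs alone do not fix the figure.

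**5. Size of the gain.** The documents give no prognostic correlations. Let ΔR² be the extra share of residual variance explained beyond the baseline outcome and the listed covariates. The standard error is multiplied by √(1 − ΔR²), and the equivalent N is 200/(1 − ΔR²). Power is for d = .4 (the pilot effect), N = 200/DEFF, and an assumed correlation of .5 between baseline and outcome.

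| ΔR² (assumed) | SE multiplier | Equivalent N | Power, DEFF 1.4 | Power, DEFF 1.8 |
|---|---|---|---|---|
| 0 | 1.000 | 200 | 78.8% | 68.2% |
| .01 | .995 | 202 | 79.2% | 68.7% |
| .02 | .990 | 204 | 79.6% | 69.1% |
| .05 | .975 | 211 | 80.8% | 70.5% |
| .10 | .949 | 222 | 82.9% | 72.8% |
| .15 | .922 | 235 | 84.9% | 75.2% |

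**6. Upper bound.** Step 5 assumes that variance between visitors falls as much as variance within them. If only the within-visitor part falls, its share of the variance of an arm mean is (1 − ICC)/DEFF: .95/1.4 = .68 at ICC .05 and .90/1.8 = .50 at ICC .10. At ΔR² = .15 the standard error then falls by 1 − √(1 − .15 × .68) = 5.2%, or 1 − √(1 − .15 × .50) = 3.8%, instead of 7.8%. At .01 the fall is about 0.3%.

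**The case against.** **Baseline adjustment already does most of the work.** This is the strongest reply, and it largely stands. Measured infant size and maternal weight at enrolment are in the Aim 1 models, so only the increment matters, and no figure in the documents shows that it is large. What remains is the argument in step 3, which for infants rests on the protocol's own premise.

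**The extra covariates are not free.** This stands. The list already has nine entries plus the baseline outcome, and the Power Analysis promises caution about the number of variables. Some pre-pregnancy values will be missing or recalled. Gestational weight gain is not among the items that the Records paragraph says come from the HVP partner, so its availability is less certain.

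**Medical history might cover them.** The fixed list includes medical history, which could be read to include earlier obesity or gestational weight gain. That reading is possible but not stated, and it would not reach birth weight.

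Three stronger readings are tempting, but the documents do not support them:
- *These variables are used nowhere.* The baseline-difference rule can admit them. What is missing is prespecified use.
- *Recall of pre-pregnancy weight during pregnancy is impossible because mothers join with a 6-month-old.* C.3 puts enrolment in HVP services before birth, and C.4 says services begin prenatally. Recall at HVP recruitment is therefore feasible and may be the same information that the HVP partner supplies.
- *Acculturation is a mandatory covariate that is never measured.* No measure is named, but the description of the demographic data is open-ended: "We will collect demographic data, including socioeconomic status (education, income, eligibility for SNAP". That is missing detail, not proof of absence.

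**Conclusion.** The point holds as a modest improvement to the prespecification. Collected variables with a plausible prognostic role should not depend on an unclustered baseline test to enter the weight and growth models. With an assumed ΔR² of .01 to .15, the standard error falls by 0.5% to 7.8%, and power for d = .4 rises by about 0.4 to 7 points. At ΔR² of .05 or less the power gain is about 2 points. These are upper figures: they assume equal reduction between and within visitors and no loss from missing values. The ΔR² range, the .5 baseline correlation and the 80% power used to match the plan's f are assumptions. A reader might infer that substantial precision is being given away at no cost; the documents do not show that. Nothing here suggests bias in the arm comparison.

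**What to change.** In C.6, General strategy, replace test-based selection for these variables with prespecified adjustment, and repeat it under Aim 1:
- **Infant growth models:** birth weight and pre-pregnancy BMI, in addition to the baseline outcome.
- **Maternal weight models:** pre-pregnancy BMI, plus gestational weight gain where the record supplies it.
- **Missing values:** the multiple imputation or full-information maximum likelihood already planned.
- **Source:** state one primary source for pre-pregnancy weight, so that C.5 and the Records paragraph read alike.

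The cost is SAP wording, one or two more covariates per model, and some missing or recalled pre-pregnancy values. If gestational weight gain needs medical-record access that is not yet arranged, it can be left out without affecting the rest.

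As a side note, name the measure for acculturation or remove it from the fixed list.

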
**C.3. Participants.** Participants will be low-income mothers/infants (6mo at enrollment) *who are already receiving services from our HVP partner (Figure 6)*. Thus, study enrollment does not require that we recruit more families than our HVP partner is already enrolling. Mothers are enrolled in HVP services through outreach and screening pre-partum, in English or Spanish, at community health centers and hospitals. In order to be eligible mothers must meet a number of (but not all) risk criteria (e.g., low-income, housing instability). Enrolled mothers are matched to a home visitor (nurse) based on culture and language. **Recruitment.** Assessment workers (distinct from home visitors delivering services) who enroll families into services will introduce the study to mothers and obtain written consent. They will clarify with mothers that their refusal to participate in the study will not affect their receipt of any other services provided by the HVP. In our experience, families feel comfortable refusing if they are not willing to participate. Mothers/infants will be ineligible if they have any of the following conditions: eating disorders (e.g., bulimia nervosa), schizophrenia, and obesity-related syndrome (e.g., Prader Willi). Participants enrolled in a weight-loss program will be ineligible. Based on our pilot work, we expect to recruit 70% Hispanic/Latino, 13% African American, 8% White, 5% American Indian/Alaskan, 4% mixed race. **Retention.** We have learned a great deal about retention through our pilot work. For instance, most attrition from HVP services occurs in the first six months of services. Therefore, to maximize retention, mothers will be invited to participate in the study *after six months of home visits*. The unique relationship between home visitors and mothers facilitates subsequent retention, as many of these mothers are socially isolated and home visitors are important confidants and supports. We will use multiple strategies that are effective for high-risk populations to further retain the study sample: (1) gift cards of \$25 at each data collection, with all incentives paid after each assessment; (2) frequent contacts to maintain engagement and foster open communication; (3) quarterly newsletters to update subjects about study activities; (4) acknowledging birthdays and milestones; (5) reminder phone calls the day before the weekly visits and assessment sessions. **Randomization.** Randomization will be at the level of home visitors, who deliver the HVP (cluster randomization). Home visitors who serve mothers that are participating in the proposed study will be randomly assigned to deliver either HVP only or HVP+COPE. Potential concerns with randomizing by home visitors are feasibly addressed in this study. First, the likelihood of

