**Statistical Models Aims 1-3.** Our conceptual model includes three types of variables: Intervention arms (HVP vs. HVP+COPE) and covariates, mediators, and outcome variables. We will use multiple statistical procedures tied to the analytic objectives of each of our specific aims, including generalized linear modeling, path analysis and structural equation modeling (SEM) approaches. To control for potential cluster effect due to home visitors as families are nested with visitor, statistical models will be developed based on multilevel path analysis to test direct and indirect (or mediational) effects hypothesized in the model. The models involve two levels with mothers or children as Level-1 units and visitors as Level-2 units treated as a random effect. With multilevel path modeling approach, the covariance matrix to be analyzed can be properly decomposed into individual- and group-level covariances to account for the clustering effect due to visitor nesting effect of the data. The multilevel path model can involve all variables from the family level in the analysis. The model can also incorporate distal predictors and mediators from the visitor-level (Level-2) and outcomes from family-level (Level-1) data. The aims of the proposed study focus on the Level-1 units. Following Bentler-Weeks modeling notation, the path model can be expressed as:  $\eta = \beta\eta + \gamma\xi$ , with all exogenous (distal) variables defined as  $\xi$  and all endogenous (mediators and final outcomes) variables as  $\eta$ . The parameters in  $\beta$  and  $\gamma$  matrices can be specified according to the hypotheses of each Aim. Models to be developed are discussed in greater detail below for each Aim. Mplus software will be used model estimation and evaluation.

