**Power Analysis Aims 1-3 (Figure 7).** A total of 30 home visitors will be recruited and randomized to HVP or HVP+COPE. With an average of 13 families served by each visitor, a total of 300 families will be invited to participate in the proposed study over 12 months. Based on our pilot work and existing HVP data, we expect a retention rate of 75% of families, which will result in a final sample of 200 mothers/infants. We have calculated power using G\*Power based on an effective sample of N=200 for the main weight related outcomes with the design of repeated measurement. All tests use a two-sided alpha level of .05. Our pilot study showed a small to medium effect size of .4 (Cohen's *d*) on our main outcome of children's weight velocity and smaller effect on energy intake at 6 months post-test. No previous study has investigated the long-term (12 months) delivery of in-home obesity prevention on 0-2yo children's growth trajectory, diet and activity. However, an in-home intervention compared to outpatient pediatric counseling resulted in a large effect size of 1.64 (Cohen's *d*) for changes in zBMI at 12 months, among obese 2-5yo children. To account for potential large clustering effect at the home visitor level, we assume the intraclass correlation (ICC) of .05 to .1 with inflation factors  $(1+(n-1)*ICC)$  of 1.4 to 1.8, respectively. After taking inflation factor into account, our proposed sample size of 200 will have enough power to detect medium effect sizes based on Cohen's *f* between .17 and .20. More comprehensive path model will be specified in each aim for model evaluation and hypothesis testing. We are aware of the sample size limitation and will be cautious in the number of variables and the size of the model involved. We used the hypothesis-testing framework of RMSEA to estimate power of model fitting in our study. With  $\alpha = .05$ , a null hypothesis RMSEA of .00 (almost exact fit for path model), an alternative hypothesis RMSEA of .08 (criterion of not acceptable models) and degrees of freedom (size of the model) ranging from 10 to 15, the range of statistical power for a sample size of 300 is between .83 and .93. We will have sufficient power to detect small to medium effect of a set of pre-selected parameters associated with mediators and outcomes with sample size of 200.

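### The Aim 1 arm effect rests on 30 randomised visitors, but the plan names no small-sample method; if tested by maximum likelihood with a z reference, the stated 5% becomes about 6% to 7.5%, and up to about 8%

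*Combined protocol and SAP*

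**What the plan says.** Section C.3 (Randomization) assigns home visitors, not families, to the arms. Section C.6 (Power Analysis Aims 1-3) gives the number: "A total of 30 home visitors will be recruited and randomized to HVP or HVP+COPE". It also sets the error rate: "All tests use a two-sided alpha level of .05".

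Section C.6 (Statistical Models Aims 1-3) describes the model: "The models involve two levels with mothers or children as Level-1 units and visitors as Level-2 units treated as a random effect". It says of Mplus that it "will be used model estimation and evaluation"; no other program is named for these models. Under Aim 1, the primary comparison uses multilevel regression, described as a path model without mediators. Under Aim 2, the intervention is placed at Level 2.

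Section C.6 (General strategy) offers multiple imputation, full-information ML, or both for missing data. Its covariates for all analyses include home visitor experience and also home visitor itself. Nowhere do the documents name REML, a reference distribution or degrees of freedom for the arm test, a permutation test, or an analysis of visitor means.

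**The concern.** Arm is constant within a visitor, so the number of families does not determine how well the error variance of the arm contrast is known. The number of visitors does. Large-sample ML inference goes wrong in two ways with 30 clusters. It takes the critical value from the normal distribution although the variance is estimated on 27 or 28 degrees of freedom, and it estimates the between-visitor variance with a downward bias. Both make intervals too narrow and p-values too small.

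At stake is the declared 5% for the primary contrasts. Aim 1 tests several maternal and infant outcomes at each follow-up and again longitudinally, so any excess recurs across many tests.

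**Working it through.** **Inputs from the documents.** 30 visitors; two-sided .05; ICC .05 to .10 (Power Analysis); visitor experience in all analyses (C.3 and General strategy). The power section works "based on an effective sample of N=200 for the main weight related outcomes", so 200/30 = 6.7 analysed families per visitor; all 300 invited families would give 300/30 = 10. The stated average of 13 families per visitor is not used, because 30 × 13 = 390 exceeds both totals.

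**Assumptions.** 15:15 allocation (the ratio is not stated); ML estimation with a z reference; one outcome with a random visitor intercept; ten family-level covariates to stand for the plan's list after dummy coding.

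**Step 1: critical value alone.** With an unbiased standard error, P(|t| > 1.96) is 6.0% on 28 df and 6.0% on 27 df. The correct critical values are 2.048 and 2.052.

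**Step 2: add the ML variance.** With equal caseloads the arm effect is a difference in visitor means. ML divides the residual sum of squares of those means by 30 rather than by 28 or 27, so rejecting at |z| > 1.96 means rejecting at |t| > 1.96 × √(df/30).
- 28 df: 1.96 × √(28/30) = 1.893, size 6.9%.
- 27 df (with experience): 1.96 × √(27/30) = 1.859, size 7.4%.

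This holds when the estimated between-visitor variance is above zero. At low ICC it is often set to zero, which makes the test less liberal, so simulation is needed.

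**Step 3: simulation under no effect.** 24,000 trials per setting; Monte Carlo standard error near 7% is √(.07 × .93/24,000) = 0.16 points.

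| Setting, 30 visitors | ML with z, ICC .05 | ML with z, ICC .10 |
|---|---|---|
| 200 families, equal caseloads, arm only | 6.2% | 6.6% |
| Same, plus visitor experience | 6.5% | 7.3% |
| Same, plus experience and 10 family-level covariates | 6.9% | 7.8% |
| 200 families, 2 to 14 per visitor, arm only | 6.7% | 7.6% |
| Same, plus experience and 10 family-level covariates | 8.0% | 8.3% |
| 300 families, equal, experience and 10 family-level covariates | 7.1% | 7.5% |

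A separate simulation with equal caseloads (100,000 trials per cell, 7 or 10 families per visitor, ICC .05 to .10) agrees: ML with z gives 6.3% to 6.7% with arm only and 6.6% to 7.3% with experience. At ICC .02 it gives about 5.4% to 5.9%, and at ICC 0 less than 5%. With the full covariate list and 200 families, the ICC .02 figure is 6.3% to 6.6%.

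**Step 4: can the stated 5% be reached?** Yes. At 200 families and ICC .05 to .10, REML with t on 27 to 28 df gives 4.4% to 5.4%, and a t-test on visitor means 4.8% to 5.2%. REML with z still gives 5.3% to 6.5%. Cluster-robust standard errors with z do not help: 6.7% to 8.2% with equal caseloads, up to 9.5% with unequal ones.

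**The case against.** The strongest objection is that the faulty test is inferred. ML appears only as a missing-data option, the link from regression to path model is permissive, and C.6 promises several procedures, including generalized linear modelling. A reader might infer that the plan prescribes a z test, or that the true error rate is simply 7% to 8%. The documents support neither. Under REML with z the excess is about a point or less in most settings. With equal caseloads and the one measured visitor-level covariate the plan names, ML with z stays near or below 7.4%; about 8% needs the longer covariate list, and the top of the range also needs unequal caseloads. The plan offers its ICC range as allowance for a potentially large clustering effect, and the excess shrinks below it. The simulations also omit baseline adjustment and repeated measures. All of this stands, and it is why the figure is conditional. What remains is that the plan names nothing that would prevent the inflation. Unequal caseloads are also plausible, given rolling enrolment, matching on language and ethnicity, and attrition.

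A reader might also infer that the power calculation fails because it ignores the 28 df. The plan's own figures largely offset this. It uses inflation factors of 1.4 and 1.8, while 6.7 families per visitor give 1 + 5.67 × .05 = 1.28 and 1 + 5.67 × .10 = 1.57. With equal caseloads that overstates the detectable effect by √(1.4/1.283) − 1 = 4.4% to √(1.8/1.567) − 1 = 7.2%. Using t on 27 to 28 df adds 3.6% to 3.8% (80% power assumed). No power criticism is made here.

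Nor do the documents say that visitor enters as fixed indicators; listing it as a covariate may only be a loose reference to the random effect.

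**Conclusion.** The concern holds in conditional form. The design gives the arm contrast 27 to 28 degrees of freedom, and the plan specifies neither an estimator nor a reference distribution that respects this. If ML with z is used at ICC .05 to .10, the type I error is about 6% to 7.5% with visitor experience as the only visitor-level covariate and roughly equal caseloads. It rises to about 8% with the full covariate list and unequal caseloads. At ICC .02 it is nearer 5.5% to 6%, or slightly above 6% with the full list. This rests on 15:15 allocation, a random-intercept model for one outcome, and an inferred test.

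This is more than missing detail, because the most natural implementation misses the stated alpha and a method that meets it is readily available. It should be corrected before analysis, but it does not threaten the design.

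**What to change.** For the Aim 1 arm contrasts, state in C.6 that they will be estimated in a linear mixed model with a random visitor effect, fitted by REML. Tests and confidence intervals should use Kenward-Roger or Satterthwaite degrees of freedom, or visitor-level t degrees of freedom (about 27 to 28). A permutation test that reassigns visitors can be added as a check. Keep Mplus for the mediation models of Aims 2 and 3. Multiple imputation, already an option in the plan, can cover missing covariates.

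In the same edit, reconcile the two statements about home visitor. The General strategy lists it as a covariate in all analyses, while Statistical Models makes it a random effect. If entered as fixed indicators it would absorb the arm effect, which could then not be estimated. Say that visitor enters as the random effect and that experience is the visitor-level covariate.

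The cost is wording; no families, visits or data are added. The critical value rises from 1.96 to about 2.05, widening intervals by 2.048/1.96 − 1 = 4.5%. Counting the REML variance as well, they are about 8% to 10% wider than under ML with z (2.048/1.893 = 1.08; 2.052/1.859 = 1.10). Nominal power falls by a few points: in one check (effect 0.45 SD, ICC .05, 7 families per visitor) it was 82% for ML with z, 80% for REML with z and 77% for REML with t. Part of that gap is only the inflated alpha of the first test.
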